9.2 Justification for the design of the clinical investigation

The device has reached the development stage where a verification of its applicability in the clinical settings is warranted. The design of the investigation is that of a safe way to test the device in clinical use without changing the standard- of-care for the participating subjects, while collecting data on possible benefits of the use of the device.

9.3 Selection of investigational population

9.3.1 Recruitment

Subjects having lesions where MM cannot be ruled out will be identified for inclusion in this CI. The subject visits the primary care clinic for examination of one or more skin lesions of concern, or the investigator detects a suspected skin lesion in connection with another cause of visitation.

²To be collected by each region's actual cost for PAD and excision or data collected via the KPP-database.

Document	Doc. id.	Version	Page	
Clinical investigation Plan / Investigation code- AI-DSMM/	GR 21- 023	01	27 (52)	_

9.3.2 Number of subjects

To reach the target of 239 eligible lesions with a PAD approximately 500 lesions will need to be included, that is up to 500 subjects. The CI needs to be able to analyse 239 PAD verified lesions where at least 12 lesions need to be PAD positive responses (confirmed MM). In case, after 500 subjects/lesions have been evaluated and the 12 positive PAD have not been obtained, further subject enrolment will continue until 12 positive PAD have been reached.

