When the subject has been fully examined and receives the final tumor diagnosis from the histopathology/PAD results (melanoma/non melanoma), the degree of agreement between the PAD and the outcome of the AI SW decision support is calculated with the Kappa-analysis and the diagnostic accuracy to be able to distinguish melanoma from non-melanoma in the form of sensitivity and specificity as well the positive and predictive value. The corresponding comparison is performed from the examining investigators' estimated clinical degree of suspicion, as well as the diagnostic accuracy when both the PAD and the AI decision support are weighted together (i.e. in cases where the investigator and the decision support are in agreement in their assessment). The clinical investigation will collect information from the users, how participating users (investigators at the site) experience the usability of the AI SW decision support and attaching applications, from short surveys including the validated System Usability Scale.

Use the same overall description given in Section 9.1.

Duration of exposure to the Investigational Medical Device

The subjects will not be in any direct contact with IMD Dermalyzer.

Duration of subjects' involvement in the investigation

The subjects will only perform 1 visit at a primary care centre to assess the cutaneous lesion(s).

Clinical performance assessments

The subject will be examined according to clinical routine. The cutaneous lesions where MM cannot be ruled out (study lesions) will be photographed with a digital dermatoscope. The digital image will then be able to be instantly uploaded to the study's AI enhanced web application (Dermalyzer), where the AI algorithm performs the image analysis within a few seconds.

Template Doc. id. Version

02

CIP Template QMS 12-01-

Document	Doc. id.	Version	Page
Clinical investigation Plan / Investigation code- AI-DSMM/	GR 21- 023	01	12 (52)

Clinical safety assessments

All considered reportable events in accordance with MDR, will be captured. The subject included in the investigation will follow the standard of care. The use of the AI will not influence the subject or the medical care of the subject.

Statistical methods

The sample size of at least eligible 239 lesions is calculated by an expected true proportion of 95% with 80% power. The estimated frequency of actual found malignant melanoma is 4.65% (or 12 MM out of 239 lesions).

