8.1.1 Primary endpoint

The primary endpoint will be measured as the true proportion; by testing if the device based on artificial intelligence (AI) gives correct results as compared with the result of the lesion analysis (the final classification by PAD) in at least a certain proportion (π) of the analyses.

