9 INVESTIGATIONAL PLAN

9.1 Overall investigational design and schedule of events

The subjects will be included from primary care centres. If the subject's lesion(s) is suspected of melanoma or melanoma cannot be ruled out the subject is asked to participate in the investigation. The investigator examines the subject's lesion(s) (with or without a dermatoscope) and may also take dermoscopy images according to standard of care. The investigator then makes his clinical

Document	Doc. id.	Version	Page	
Clinical investigation Plan / Investigation code- AI-DSMM/	GR 21- 023	01	23 (52)	_

assessment of the subject lesion(s) based on established clinical decision algorithms (such as "Chaos and clues", "3- or 7-point checklist", or the ABCDE criteria) of whether there is a suspicion of melanoma, according to the usual clinical routine (also includes very low suspicion that cannot be completely dismissed). The investigator decides on action based on his or her MM suspicion (excision at the primary care centre or referral for excision or referral to a dermatologist for further assessment), see figure 1.

If the subject has agreed to participate in the investigation, the investigator indicates in the eCRF his clinical suspicion level of MM and decided action.

The investigator takes images of the lesion(s) again, this time with a mobile phone, containing the IMD AI SW, connected to a dermatoscope, and follows the on-screen instructions, see appendix 13.3. The image is processed by the AI SW and the results are visible on the screen within seconds. A unique auto generated code number is also presented. The code number is registered on the enrollment log and in the eCRF. The investigator records how he considers that the degree of suspicion of MM (higher vs lower) would have been affected by the AI SW result if it had been the governing body for the treatment. When the PAD result is available the outcome is documented in the eCRF.

Figure 1. Investigator workflow for assessing MM suspicion and action to be taken

[figure not shown]

02

AI MEDICAL TECHNOLOGY AIM AB

Document Doc. id. Version Page

Clinical investigation Plan / Investigation code- AI-DSMM/ GR 21- 023 01 24 (52)

Visits and assessments will be performed as described in Table 9.1. Each assessment is further described in Section 9.5.

DocumentDoc. id.VersionPageClinical investigation Plan / Investigation code- AI-DSMM/GR 21- 0230125 (52)

Table 9.1 Schedule of events

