9.5.3 Laboratory assessments

Histopathology results (PAD) from excised lesions according to standard routine.

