9.7.6 Determination of sample size

The general practitioner (GP) will only include subjects in the investigation with lesions where melanoma cannot be ruled out. All lesions where melanoma cannot be ruled out will be sent for an analysis (final classification) to confirm – or not confirm – if the suspected melanoma is a melanoma or not. Each lesion where melanoma cannot be ruled out will be analysed by the IMD and the IMD will classify each lesion where melanoma cannot be ruled out as "Low Risk of being a melanoma" (Low) or "High risk of being a melanoma" (High).

In Table 1 the possible outcomes are described and (A+D)/(A+B+C+D) is the proportion of correct classifications by the IMD.

Template Doc. id. Version

CIP Template QMS 12-01- 02
01

Document Doc. id. Version Page

Clinical investigation Plan / Investigation code- AI-DSMM/ GR 21- 023 01 40 (52)

Table 1 Outcome (m = number of patients) for a binary variable where two groups of observations are linked together.					
			The Al device		
		High	Low	Total	
Final classification	Melanoma	А	В	A+B	
	Not melanoma	С	D	C+D	
	Total	A+C	B+D	A+B+C+D	

The expected value of (A+D)/(A+B+C+D) is denoted π and then the hypotheses of interest are

 H_0 : $\pi \leq \pi_0$

 H_1 : $\pi > \pi_0$

The null-hypothesis (H₀) will be rejected if the one-sided p-value is less than a. If $\pi = \pi_1$ the power to reject H₀ should be β .

Typically, a = 2.5 % and β = 80 % or 90 %. The p-value will be calculated using the exact Binomial test.

In a successful investigation H_0 is rejected and then H_1 is accepted.

Document Doc. id. Version Page

Clinical investigation Plan / Investigation code- AI-DSMM/ GR 21- 023 01 41 (52)

In Table 2 the needed number of lesions is presented based on the formula above and for statistical power 90%.

Table 2	Number of lesions where melanoma cannot be ruled out needed to achieve 80% power to reject (i.e. get a one-sided p-value less than 2.5%) the null-hypothesis by proportions to be rejected (i.e., π_0) and by assumed true proportions (i.e. π_1). Calculated by Sample Size a single proportion V01.xls.					
True Proportion (π ₁)		Р	roportion to b	oe rejected (π	:0)	
(71)	50%	60%	70%	80%	90%	95%
55%	783					
60%	194					
65%	85	742				·
70%	47	182				
75%	29	78	638			
80%	20	43	153			·
85%	14	26	64	471		·
90%	10	17	34	108		
95%	7	11	19	42	239	

Document			Doc. id.	Version	Page	
Clinical investigation Plan / Investigation code- AI-DSMM/		GR 21- 023	3 01	42 (52)		
100%	4	6	9	16	35	73

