11.2 Time table

The end of the clinical part of the investigation is defined as the enrolment of approximately 500 lesions where MM could not be ruled out, to reach the target of 239 evaluable (having PAD outcome result) lesions, with 12 positive PAD results. It is estimated that the PAD results will come from the laboratory within approximately 2 months time frame from each excision.

The enrolment period of the investigation is expected to start in Quarter 1, 2022 and to be completed by Quarter 3, 2022.

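### About 500 lesions are planned to yield 239 with PAD although 9.7.6 sends every lesion for final classification; the gap is unexplained and the PAD-only analysis is implied but never stated as a rule

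*Combined protocol and SAP*

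**What the plan says.** All references are to the combined protocol and SAP.

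- **Everyone is verified.** Section 9.7.6: "All lesions where melanoma cannot be ruled out will be sent for an analysis (final classification". Section 8.1.1 identifies the reference standard as "the final classification by PAD". Inclusion (9.3.4) requires such a lesion, so on a plain reading every included lesion should have a PAD.
- **About half are verified.** Section 9.3.2: "To reach the target of 239 eligible lesions with a PAD approximately 500 lesions will need to be included". Section 11.2 repeats the plan: about 500 lesions, "to reach the target of 239 evaluable (having PAD outcome result) lesions, with 12 positive PAD results". The synopsis makes 239 a minimum: "The sample size of at least eligible 239 lesions".
- **How a lesion might lack a PAD.** Section 9.1: "The investigator decides on action based on his or her MM suspicion". The options are excision at the centre, or "referral for excision or referral to a dermatologist for further assessment". Section 9.5.3 lists "Histopathology results (PAD) from excised lesions according to standard routine".
- **Analysis.** The primary endpoint in 9.7.6 is (A+D)/(A+B+C+D), and each of the four cells needs a final classification. The ITT set in 9.7.5 takes all correctly included subjects and sets no condition on PAD. The PP criteria are still to be defined. Section 9.7.3.2 refers additional analyses to an SAP; no separate SAP text was supplied.

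**The concern.** The primary objective (8.1, 9.7.3.1) covers lesions at every level of suspicion, but only lesions with a PAD can enter the four-cell table. If lesions under low suspicion are less often excised, and the device performs differently on them, accuracy among verified lesions answers a narrower question than the one asked. Enrolling more lesions, as 9.3.2 allows, makes the estimate more precise but does not remove such a difference.

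The protocol gives no expected PAD rate, no reason for the shortfall, no alternative reference standard for lesions without PAD, and no table from which a reader could judge whether selection had occurred.

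**Working it through.** **1. The plan's own figure.** Inputs: π₀ = 90% (read from the Table 2 column that holds 239), π₁ = 95%, one-sided 2.5%, power 80% (Table 2 title and synopsis).

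n = [(1.960·√(0.90·0.10) + 0.842·√(0.95·0.05)) / 0.05]² = 238.03, rounded up to 239. The figure reproduces.

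The exact binomial test named in 9.7.6 rejects at n = 239 when 225 or more are correct (p = 0.0162 at 225; 0.0293 at 224). Its power at 95% is 78.1%.

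**2. The implied PAD rate.** 239/500 = 47.8%; 500 − 239 = 261 lesions (52.2%) without a usable PAD. This holds only if both planning figures are met, since 239 is a minimum and 500 is approximate.

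**3. Could the 12-melanoma target explain 500?** Sections 9.3.2 and 11.2 also require 12 PAD-positive lesions. With the synopsis frequency of 4.65%, the binomial chance of at least 12 is:

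| Lesions with PAD | Chance of 12 or more |
|---|---|
| 239 | 43% |
| 258 (= 12/0.0465) | 54% |
| 388 | 95% |
| 457 | 99% |

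A margin for melanomas could therefore account for a total near 500 even with full verification. However, 9.3.2 ties the 500 to reaching 239 lesions with PAD and treats a shortfall of melanomas separately, by enrolling beyond 500. This is a possible explanation, not a stated one.

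**4. What the unverified lesions could do to the result** (assuming 500 included and 239 verified).

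- At the rejection threshold, 225/239 = 94.1%. Accuracy over all 500 is 90% when 450 are correct, so the break-even in the unverified lesions is (450 − 225)/261 = 86.2%.
- With 227 correct (95%), the extreme bounds over all 500 are 227/500 = 45.4% and (227 + 261)/500 = 97.6%.
- If half the gap (131 lesions) is ineligible images, 369 eligible lesions remain, 130 of them unverified: 227/369 = 61.5% and (227 + 130)/369 = 96.7%.
- If 300 of 500 have PAD and 95% of these are correct: 285/500 = 57.0% and 485/500 = 97.0%. If 400 have PAD: 380/500 = 76.0% and 480/500 = 96.0%.

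**5. Sensitivity.** If 12 of 12 verified melanomas are flagged, then 1, 2 or 3 unverified melanomas classified Low would give 12/13 = 92.3%, 12/14 = 85.7% or 12/15 = 80.0%. With so few events, each unverified melanoma matters.

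**The case against.** The strongest reply has four parts.

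**The plan does imply how these lesions are handled.** Section 11.2 equates evaluable with having a PAD result, 9.3.2 speaks of analysing 239 PAD-verified lesions, and the endpoint is agreement with PAD. This stands. A reader might infer that the text is silent on lesions without PAD, and that goes too far: a complete-case analysis is implied. It appears as a recruitment target, though, not as a rule in 9.7.5, and it does not fit the ITT definition.

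**The gap may be harmless.** Section 9.3.2 counts eligible lesions, and 9.3.5 (items 8 and 9) excludes incomplete or unfocused images, which is an eligibility loss and not missing verification. Withdrawals, pending PADs and a margin for 12 melanomas may add to it. This also stands. One might infer that about 261 lesions go unexcised, or that only unusable images could reconcile the sections. The documents support neither.

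**No bias is shown.** The investigator's assessment is recorded before the AI image (9.4.10), the AI result is not meant to influence care (5.5.1), and referral to a dermatologist does not rule out later excision. This stands against any claim that verification bias is established. What remains is an indirect route: suspicion can affect excision, and device performance can vary with suspicion.

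**The SAP may deal with it.** That cannot be ruled out. The point is therefore limited to the supplied text.

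It is also fair that the extreme bounds are not forecasts: 45.4% requires every unverified lesion to be misclassified.

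**Conclusion.** The point holds in this limited form. Read plainly, 9.7.6 conflicts with 9.3.2 and 11.2, the reason for the gap is not given, and the PAD-only analysis is implied but not stated as a rule. The design leaves a route by which PAD availability may depend on suspicion, so the primary result may not represent the stated target.

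The conflict between the sections is certain. The size and direction of any bias are unknown: the documents give no PAD rate and no device performance by suspicion level, and there is no bias from this source if PAD availability is unrelated to suspicion. The break-even of 86.2% and the range 45.4% to 97.6% rest on exactly 239 of 500 being verified, and the range shrinks as the gap closes or proves to be ineligible images. The change should be made because it affects what the trial can conclude and costs little; it does not invalidate the primary test in PAD-verified lesions.

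**What to change.** 1. Reconcile 9.7.6 with 9.3.2 and 11.2, and state what the difference between 500 and 239 consists of. Which clinical pathway applies is for the sponsor to state.
2. State in 9.7.5 that the primary analysis uses PAD-verified lesions, and limit its conclusion to them.
3. Record for each lesion why there is no PAD: image ineligible, assessed but not excised, PAD missing or pending, or withdrawn. Sections 9.3.3 and 9.8 already ask for a subject-level withdrawal reason and a not-done entry, but not for this.
4. Tabulate suspicion level, decided action and AI result by PAD status for all eligible imaged lesions.
5. Prespecify a supportive sensitivity analysis of accuracy and specificity: best- and worst-case bounds, plus verification weighting on AI result and suspicion, bootstrapped by subject. For sensitivity, with roughly 12 melanomas, report bounds only.
6. If the SAP already does this, cross-refer to it from 9.7.5.

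**Cost.** Protocol and SAP wording, one eCRF field and modest programming; suspicion, action and AI result are already collected. The drawbacks are wide bounds, perhaps too wide to act on if the gap stays near half, and an untestable assumption in the weighting: that verification is independent of disease status given the recorded variables. A dermatologist's later examination could violate it, which is why the analysis should stay supportive.

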9.3.3 Screening and enrolment log

Each clinic will keep a log of all subjects screened and included. The reason for screening failure should be stated for all subjects screened but not included. The reason for withdrawal should be stated for all subjects included but not completed.

9.3.4 Inclusion criteria

For inclusion in the investigation, subjects must fulfil all the following criteria:

- 1. Patients ≥18 years
- 2. Patients attending a healthcare facility with at least 1 suspicious skin lesion where MM cannot be ruled out.
- 3. Willingness and ability to provide informed consent.

9.3.5 Exclusion criteria

Subjects must not enter the investigation if any of the following exclusion criteria are fulfilled:

- 1. Cutaneous lesions that are considered as benign by the investigator and thus not subject for further clinical investigation
- 2. Cutaneous lesions in areas that are not suitable for dermoscopic imaging
- 3. Cutaneous lesions in areas with any form of scarring of tissue due to injury
- 4. Damaged or injured non intact skin where the cutaneous lesion is located
- 5. Individuals with skin type V and VI according to the Fitzpatrick scale (darker brown or black coloured skin)

Template Doc. id. Version

02

Document	Doc. id.	Version	Page	
Clinical investigation Plan / Investigation code- AI-DSMM/	GR 21- 023	01	28 (52)	

- 6. Cutaneous lesions in areas covered by tattoos
- 7. Cutaneous lesions in abundantly hairy skin areas (provided the area cannot be shaved freely from the hair to allow clear view for the dermatoscope)
- 8. Images where the entire lesion is not inside the photo
- 9. Images that are out of focus

9.3.6 Criteria and procedures for subject withdrawal

An investigational subject should be withdrawn from the intervention if, in the opinion of the Investigator, it is medically necessary, or if it is the expressed wish of the subject. In this CI the subjects only participate a short time at one visit however a subject can always at any time withdraw consent.

9.4 Investigational Medical Device description

9.4.1 General description

Dermalyzer is an image analysing software application functioning as decision support to healthcare professionals on assessing suspected cutaneous lesions for skin cancer. The device should be used in combination with a medical professional assessment of the suspected lesion. The software application uses a mobile camera to capture images of cutaneous lesions.

9.4.2 Intended use

The device is intended to be used as a decision support system for assessing cutaneous lesions suspected of being melanomas. The input from the device is not intended to be used as the sole source of information for diagnosis. The device should be used in combination with a medical professional assessment of the suspected lesion. The service does not provide any other diagnostic use.

9.4.3 IMD classification

Non CE marked Medical Device Software (MDSW) class IIb.

Template Doc. id. Version

CIP Template QMS 12-01- 02

CIP Template QMS 12-01-

Document	Doc. id.	Version	Page	
Clinical investigation Plan / Investigation code- AI-DSMM/	GR 21- 023	01	29 (52)	_

9.4.5 Summary description of the IMD

An overview picture of the IMD is given in Figure 3.

[figure not shown]

Figure 3 - Overview of the Investigational Medical Device - Dermalyzer Clinical Decision Support System

9.4.6 Intervention procedure

Dermalyzer shall be used by medical professionals in primary care settings. The software shall be used as a decision support system to assess cutaneous lesions on patients aged 18 or more having suspicious melanoma lesions.

 Template
 Doc. id.
 Version

 CIP Template
 QMS 12-01-01
 02

Document	Doc. id.	Version	Page	
Clinical investigation Plan / Investigation code- AI-DSMM/	GR 21- 023	01	30 (52)	

Detailed Instructions for use (IFU) are included in Appendix 13.3.

9.4.7 Packaging, labelling and storage of the Investigational Medical Device

For the clinical investigation, the application Dermalyzer from Google Play or App Store is already downloaded on a compatible Android or iOS mobile device. Operating system compatibility for iOS is 13.0 and later and Android is Pie 9 (API Level 28) and later. Dermatoscopic adaptors will be used connected to the phone. The sites can have different types of smartphones and versions will be captured in the eCRF. The application Dermalyzer log-in screen is marked "Use only for Clinical Investigation", see Figure 4.

Figure 4. Dermalyzer Log-in Screen

9.4.8 Compliance with IMD usage

The IMD must be used according to the IFU, see Appendix 13.3.

9.4.9 Accountability/traceability of the Investigational Medical Device

The accountability of the IMD will be documented both which mobile phones that will be provided to which site but also which version of the device that is applied. The sponsor-investigator or delegated personnel is responsible to ensure traceability. Each site will be provided with a phone

 Template
 Doc. id.
 Version

 CIP Template
 QMS 12-01-01
 02

Document	Doc. id.	Version	Page	
Clinical investigation Plan / Investigation code- AI-DSMM/	GR 21- 023	01	31 (52)	

with a unique sim-card and each phone will have a unique IMEI number. The phones sent to each site will be controlled and locked to only allow certain functions, which means that full control, over all software installed on the phones in general and which version of the software that is installed on each device in particular, can be achieved. The dermatoscope model that will be used as attachments to the phones during the investigation is the DermLite D3 and Heine iC1/7.

